10.4.3 HANDLING OF ADVERSE EVENTS

All adverse events resulting in discontinuation from the study should be followed until resolution or stabilization. Subjects should be followed for AEs for 30 calendar days (+/-7 days) after discontinuation or completion of protocol-specific treatment (umbralisib). All new AEs occurring during this period must be reported and followed until resolution unless, in the opinion of the investigator, these values are not likely to improve because of the underlying disease. In this case, the investigators must record his or her reasoning for this decision in the subject's medical record and as a comment on the eCRF. After 30 days, only AEs, SAEs, or deaths assessed by the investigator as treatment related are to be reported.

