4.4 DISCONTINUATION FROM STUDY TREATMENT

Patients will be discontinued from study treatment for any of the following reasons:

- Disease progression
- Intolerable toxicity related to study drug
- · Patient requests to withdraw consent or discontinue treatment
- Pregnancy
- Inability of the patient to comply with study requirements
- · Conditions requiring therapeutic intervention not permitted by the protocol
- Non-compliance/lost to follow-up
- Investigator discretion
- · Discontinuation of the study by the Sponsor

Patients who discontinue from study treatment (for reasons other than progressive disease) should continue to be followed for progression as per the Study Assessment Table.

After withdrawal from protocol treatment, patients should be followed for AEs for 30 calendar days after their last dose of study drug. All new AEs occurring during this period must be reported and followed until resolution, unless, in the opinion of the investigator, these values are not likely to improve because of the underlying disease. In this case the investigators must record his or her reasoning for this decision in the patient's medical records and as a comment on the electronic Case Report Form (eCRF).

All patients who have CTCAE Grade 3 or 4 laboratory abnormalities at the time of withdrawal should be followed until the laboratory values have returned to Grade 1 or 2, unless in the opinion of the investigator, it is not likely that these values are to improve because of the underlying disease. In this case, the investigator must record his or her reasoning for making this decision in the patient's medical records and as a comment on the eCRF.

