⁶ Baseline CT scan within 30 days prior to Cycle 1/Day 1; then during cycles 3, 6, 9, 12 and at least every 6 cycles for 24 cycles, then every 12 cycles thereafter or more frequent if warranted (+/- 14 days). CT imaging should be performed at EOT visit if it hasn't been completed within past 30 days.

⁷ If discontinued due to reasons other than progression, follow up every 3 months on status of disease progression. Patients who discontinue from study

⁷ If discontinued due to reasons other than progression, follow up every 3 months on status of disease progression. Patients who discontinue from study treatment after cycle 12 (for reasons other than disease progression) should be followed for progression, approximately every 6 months for 24 months then every 12 months or more frequent if warranted.

⁸ Serum pregnancy test within 72 hours prior to starting treatment on Cycle 1 / Day 1.

⁹ Urine pregnancy test within 72 hours of Day 1 of each cycle. Administer test with each drug dispensation after Cycle 6.

¹⁰ Peripheral Blood (screening, Cycle 2/Day 1 and at disease progression) and buccal swab (screening only) samples for correlative analyses. See lab manual.

¹¹ Additional peripheral blood sample will be collected at screening only and analyzed at central lab for high-risk cytogenetics as well as BTK/PI3K resistance and activating mutations/deletions of prognostic value.

¹² Bone Marrow aspirate/ biopsy performed at baseline at the discretion of investigator to evaluate cytopenias. Bone marrow to be repeated if patient meets clinical criteria for CR to confirm this finding, as per iwCLL criteria.

¹³ Subjects who discontinue study drug should have a follow up visit or telephone call to assess for AEs. This should be done 30 days (+/- 7 days) after the last dose of study drug. In addition, SAEs will be reported for 30 days after the last dose of study drug.

Laboratory assessments will be collected as specified in the study assessments and treatment schema. Please refer to the study/lab manual for instructions outlining collection and shipment procedures for lab samples for central review.

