9.9 STATISTICAL ANALYSES

9.9.1 PRIMARY EFFICACY VARIABLE - PFS

The primary efficacy outcome is progression-free survival (PFS). Time to progression event "Survival" curve will be presented using Kaplan-Meier method. Median time to event and the 95% confidence interval of the median times will be presented, if estimable. Median time to event will be tested against the null hypothesis value using a one-sample (one-sided) log-rank test.

PFS is defined as the interval from Cycle 1/Day 1 to the earlier of the first documentation of definitive disease progression or death from any cause.

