10.8.3 DEATHS

Deaths that occur during the protocol-specified AE reporting period that are attributed by the investigator solely to progression of the subject's CLL will not be reported as an Adverse Event. All other on-study deaths, regardless of attribution, will be recorded on an SAE Report Form and expeditiously reported to the Sponsor.

When recording a serious adverse event with an outcome of death, the event or condition that caused or contributed to the fatal outcome should be recorded as the single medical concept on the Adverse Event page of the eCRF. If the cause of death is unknown and cannot be ascertained at the time of reporting, record "Death NOS" on the eCRF Adverse Event page.

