Any secondary (occurring as a direct result as study drug administered, including but not limited to MDS) or second primary (unrelated, new cancer, including but not limited to MDS and MPD) malignancy event must be reported via the SAE form (in addition to the routine AE reporting mechanisms). Any malignancy possibly related to cancer treatment should also be reported via the routine reporting mechanisms outlined in the protocol.

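### Section 10.4.3 limits death reporting after 30 days off drug to treatment-related deaths, and no passage clearly requires the other deaths that PFS and DOR count

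*Combined protocol and SAP*

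**What the plan says.** **Endpoint.** Section 9.9.1 ends PFS at "the earlier of the first documentation of definitive disease progression or death from any cause". Sections 2.2 and 9.9.2.3 give DOR the same terminal event. Neither definition restricts deaths by cause or by time since last dose.

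**Follow-up off treatment.** Under Section 4.4, subjects who stop for a reason other than progression "should continue to be followed for progression as per the Study Assessment Table". Footnote 7 of the Section 5 schedule gives the content: "If discontinued due to reasons other than progression, follow up every 3 months on status of disease progression". Those who stop after Cycle 12 are seen about every 6 months and later every 12. Section 6.5 makes this follow-up subject to the subject's agreement. The schedule has no survival or vital-status row.

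**Reporting after day 30.** Section 10.4.3 states: "After 30 days, only AEs, SAEs, or deaths assessed by the investigator as treatment related are to be reported". Section 10.5.2 likewise places SAEs between Cycle 1/Day 1 and the end of the 30-day follow-up.

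**Other text on deaths.** Section 10.8.3 opens with "Deaths that occur during the protocol-specified AE reporting period" and exempts those due solely to CLL progression. It then asks that every other on-study death go on an SAE form whatever its attribution, without defining on-study. Section 9.7 has each subject placed in a category, three of which are early deaths (from disease, toxicity or another cause). Section 12.5 mentions vital status only for subjects who revoke authorization.

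**Second cancers.** Section 10.8.6 says that any "second primary (unrelated, new cancer, including but not limited to MDS and MPD) malignancy event must be reported via the SAE form", with no end date.

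**The concern.** A subject who stops umbralisib without progression and dies some months later of a cause judged unrelated has had a PFS event and, if a responder, a DOR event. The one sentence that expressly addresses deaths after day 30 does not ask for that death. The scheduled contacts ask about progression. Section 10.5.2 names an eCRF route for unrelated CLL progression, but no route is named for a death without progression.

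If such a death is missed and the subject is treated as censored, the error runs one way: fewer observed events and longer apparent PFS and DOR. The trial has one arm and tests the PFS median against a fixed value, so no control group shares the loss.

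**Working it through.** **1. The passages side by side.**

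| Question | Where | Answer |
|---|---|---|
| Does an unrelated death at month 5 off drug, without progression, count for PFS? | 2.2, 9.9.1 | Yes |
| Is the subject still in follow-up? | 4.4, 6.5, footnote 7 | Yes, if agreeable, for progression status |
| Must the death be reported as safety data? | 10.4.3 | No |
| Must it be reported as an on-study death? | 10.8.3 | Yes if on-study includes follow-up, which contradicts 10.4.3; otherwise no |
| Must it be entered as an efficacy event? | 9.7, 9.9.1 | Implied, but no sentence tells the site to collect it |

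**2. The plan's own figure.** The synopsis (Statistics) gives 50 analysable subjects, medians of 12 against 8 months, a one-sided 5% one-sample log-rank test, 12 months' accrual, 24 months' follow-up and 82% power. I assume exponential PFS and uniform accrual, with 24 months' follow-up after the last entry.

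- Hazards: h0 = ln 2/8 = 0.0866 and h1 = ln 2/12 = 0.0578 per month.
- P(event) = 1 − [exp(−24h) − exp(−36h)]/(12h).
- Null: 1 − (0.125 − 0.0442)/1.040 = 0.922, so 50 × 0.922 = 46.1 events.
- Alternative: 1 − (0.25 − 0.125)/0.693 = 0.820, so 41.0 events.
- Power: Φ(√41.0 × ln 1.5 − 1.645) = Φ(0.95) = 82.9%; simulation of the test gives 83.4%. The stated 82% is reproduced to within 2 points.

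**3. Effect of one lost death.** The statistic is Z = (O − E)/√E, where E is h0 times total follow-up. A lost death removes 1 from O. If the subject is censored g months earlier, it also removes h0 × g from E. With 3-monthly contacts g averages 1.5, so the net shift is 1 − 0.0866 × 1.5 = 0.87 of an event in the drug's favour. Longer gaps reduce the shift (g = 6: 1 − 0.52 = 0.48) but do not reverse it.

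**4. Illustration over an assumed range.** The documents give no lost fraction. Each setting used 40,000 simulated trials of 50 subjects at the null median of 8 months, with administrative censoring at 24 to 36 months. A random share of events was recoded as censored at the last 3-monthly contact; the 20% setting instead used a random point up to 3 months before. Rejection was at Z < −1.645.

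| Share of events lost | Deaths lost (share × 46.1) | One-sided rejection | Mean estimated median, months |
|---|---|---|---|
| 0% | 0 | 4.0% | 8.03 |
| 2% | 0.9 | 5.1% | 8.18 |
| 5% | 2.3 | 7.7% | 8.43 |
| 10% | 4.6 | 13.3% | 8.84 |
| 20% | 9.2 | 31.7% | not computed |

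With the random censoring point, the 0%, 5% and 10% settings gave 4.2%, 7.7% and 13.3%.

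Hand check at 5%: O = 43.8 and E = 46.1 − 2.3 × 0.13 = 45.8, so the mean of Z is −2.0/6.77 = −0.30. The normal approximation then gives Φ(−1.35), about 9%. The simulated 7.7% is lower because this form of the test is slightly conservative (about 4% with no loss).

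**The case against.** The strongest reply is that Section 10.4.3 governs safety reporting and says nothing about efficacy data. PFS is defined by death from any cause, Section 13.3 makes the eCRF the instrument for all data, and Section 9.7 needs deaths with their cause. Section 10.8.3, the section on deaths, disregards attribution. Section 10.5.2 lists events on study separately from those within 30 days of last treatment, so on-study may well reach into follow-up. A site asking about progression every 3 months would ordinarily learn of a death.

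Most of this stands. It defeats the reading, which 10.4.3 invites, that sites are told not to record these deaths: the text does not say so, and the eCRF pages are not in the documents. It does not supply the missing instruction. Early in Section 9.7 and on-study in Section 10.8.3 are undefined, and the wider reading of 10.8.3 contradicts 10.4.3.

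It is also fair that the simulation removes events at random from all PFS events. The gap reaches only deaths that come before any progression, occur more than 30 days off drug, are judged unrelated and go unrecorded despite follow-up. At about one such death the error is essentially nominal.

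A reader might also infer a safety gap from the contact timing: "This should be done 30 days (+/- 7 days) after the last dose of study drug" permits a call on day 23. The documents do not support making much of this, because footnote 13 keeps SAEs reportable for the full 30 days and footnote 7 contacts follow for subjects without progression.

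**Conclusion.** The point holds as a conflict of wording that bears on the primary endpoint. A stated rule limits late deaths to treatment-related ones, the endpoint counts all deaths, and nothing clearly requires the remainder to be recorded. Section 10.4.3 also conflicts with 10.8.3 on one reading, and with the requirement in 10.8.6 for second primary malignancies that are by definition unrelated.

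The direction of any bias is clear, provided a missed death is treated as censored. That is an assumption, since Sections 9.8 and 9.9.1 state no PFS censoring rule. The size is not known. The one-sided error of about 5%, 8% or 13% is what about 1, 2 or 5 lost deaths among 46 events would produce; it is not a forecast.

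Two stronger readings should be resisted. One is that the type I error of this trial is inflated: no figure in the documents shows that any death would be lost. The other is that the gap falls on the very group the trial was set up to study. The trial population is intolerant to a prior BTK or PI3K-delta inhibitor, whereas the gap touches anyone who stops umbralisib without progression, for whatever reason.

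**What to change.** - **Section 10.4.3:** apply the relatedness limit after 30 days to non-fatal AEs and SAEs only. State that the date and cause of every death, regardless of attribution, are entered on the eCRF until progression, withdrawal of consent or end of study.
- **Section 10.8.3:** define on-study to match that period.
- **Section 5, footnote 7:** add vital status and date of death to the existing follow-up contacts.
- **Sections 10.4.3 and 10.8.6:** reconcile the post-30-day limit with the second-malignancy rule and state how long that rule applies.

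The 30-day contact window need not change. The cost is amendment wording and a small eCRF addition at contacts that already take place. Sample size and power are unaffected. The downside is slightly more event recording and possibly a shorter reported PFS.

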10.5.1 DEFINITIONS OF SERIOUS ADVERSE EVENTS

The definitions of serious adverse events (SAEs) are given below. The investigator is responsible for ensuring that all staff involved in the study are familiar with the content of this section.

An SAE or reaction is defined as any untoward medical occurrence that:

- results in death,
- immediately life-threatening,
- requires at least a 24-hour in-patient hospitalization or prolongation of existing hospitalization,
- results in persistent or significant disability/incapacity, and/or
- causes a congenital anomaly/birth defect.

Medical and scientific judgment should be exercised in deciding whether expedited reporting is appropriate in other situations, such as important medical events that may not be immediately life-threatening or result in death or hospitalization, but may jeopardize the subject or may require intervention to prevent one of the other outcomes listed in the previous definition. These should also usually be considered serious. Examples of such events are intensive treatment in an emergency room or at home for allergic bronchospasm; blood dyscrasias or convulsions that do not result in hospitalization; or development of drug dependency or drug abuse.

Progression of malignancy (including fatal outcomes), if documented by use of appropriate method (for example, as per IWCLL Hallek et al. 2008), should not be reported as a serious adverse event.

A suspected unexpected serious adverse reaction (SUSAR) is defined as an SAE that is suspected to be at least possibly related to study medication and is an unexpected event. SUSAR reporting is encompassed within SAE reporting guidelines as defined in this section.

Treatment within or admission to the following facilities is not considered to meet the criteria of "inpatient hospitalization" (although if any other SAE criteria are met, the event must still be treated as an SAE and immediately reported):

- Emergency Department or Emergency Room
- Outpatient or same-day surgery units
- Observation or short-stay unit
- Rehabilitation facility
- Hospice or skilled nursing facility
- Nursing homes, Custodial care or Respite care facility

Hospitalization during the study for a pre-planned surgical or medical procedure (one which was planned prior to entry in the study), does not require reporting as a serious adverse event to the Sponsor.

TGR-1202-201-CLL

10.5.2 SERIOUS ADVERSE EVENT REPORTING BY INVESTIGATORS

It is important to distinguish between "serious" and "severe" adverse events, as the terms are not synonymous. Severity is a measure of intensity; however, an AE of severe intensity need not necessarily be considered serious. For example, nausea which persists for several hours may be considered severe nausea, but may not be considered an SAE. On the other hand, a stroke which results in only a limited degree of disability may be considered only a mild stroke, but would be considered an SAE. Severity and seriousness should be independently assessed when recording AEs and SAEs on the eCRF.

Adverse events classified by the treating investigator as serious require expeditious handling and reporting to the Sponsor in order to comply with regulatory requirements. Serious adverse events may occur at any time from Cycle 1/Day 1 through the 30-day follow-up period after the last study treatment. Sponsor or designee should be notified of all SAEs, regardless of causality, within 24 hours of the first knowledge of the event by the treating physician or research personnel.

To report an SAE, see the appropriate form.

All SAEs (regardless of causality assessment) occurring on study or within 30 days of last study treatment should be immediately reported to the sponsor as SAEs within the CRF and followed until resolution (with autopsy report if applicable).

CLL progression or death due to CLL progression should be reported by the investigator as a serious adverse event only if it is assessed that the study drugs caused or contributed to the CLL progression (i.e. by a means other than lack of effect). Unrelated events of CLL progression should be captured on the appropriate eCRF.

The investigator must review and sign off on the SAE data on the SAE report. The SAE should be reported to the Sponsor (or Sponsor designee) at [contact] within 24 hours of the first knowledge of the event by the treating physician or research personnel.

..

When an SAE is reported to the sponsor or designee, the same information should be entered on the eCRF within 24 hours (1 business day). Transmission of the SAE report should be confirmed by the site personnel submitting the report.

Follow-up information for SAEs and information on non-serious AEs that become serious should also be reported to the sponsor or designee as soon as it is available; these reports should be submitted using the appropriate SAE form.

Investigators must report SAEs and follow-up information to their responsible Institutional Review Board (IRBs)/Independent Ethics Committee according to the policies of the responsible IRB (Research Ethics Committee).

10.6 SPONSOR SAE REPORTING REQUIREMENTS

TGR-1202-201-CLL

Sponsor is responsible for reporting relevant SAEs to the competent authority, other applicable regulatory authorities, and participating investigators, in accordance with ICH guidelines, FDA regulations, and/or local regulatory requirements.

Sponsor is responsible for reporting unexpected fatal or life-threatening events associated with the use of the study drugs to the regulatory agencies and competent authorities within 7 calendar days after being notified of the event. The Sponsor will report all related but unexpected SAEs including non-death/non-life-threatening related but unexpected SAEs (SUSAR) associated with the use of the study medications to the regulatory agencies and competent authorities by a written safety report within 15 calendar days of notification. Following the submission to the regulatory agencies and competent authorities, Investigators and trial sites will be notified of the SUSAR. Investigators must report SUSARs and follow-up information to their responsible Institutional Review Board (IRBs)/Independent Ethics Committee according to the policies of the responsible IRB (Research Ethics Committee).

10.7 RECORDING OF ADVERSE EVENTS AND SERIOUS ADVERSE EVENTS

Investigators should use correct medical terminology/concepts when recording AEs or SAEs on the SAE Report Forms and AE eCRF. Avoid colloquialisms and abbreviations.

All AEs, including those that meet SAE reporting criteria, should be recorded on the AE eCRF; AEs that meet the definition of an SAE should additionally be reported.

10.8 DIAGNOSIS VS. SIGNS AND SYMPTOMS

All AEs should be recorded individually in the subject's own words (verbatim) unless, in the opinion of the Principal Investigator or designated physician, the AEs constitute components of a recognized condition, disease, or syndrome. In the latter case, the condition, disease, or syndrome should be named rather than each individual sign or symptom. If a constellation of signs and/or symptoms cannot be medically characterized as a single diagnosis or syndrome at the time of reporting, each individual event should be recorded as an AE or SAE as appropriate on the relevant form(s) (SAE Report Form and/or AE eCRF). If a diagnosis is subsequently established, it should be reported as follow-up information is available. If a diagnosis is determined subsequent to the reporting of the constellation of symptoms, the signs/symptoms should be updated to reflect the diagnosis.

10.8.1 PERSISTENT OR RECURRENT ADVERSE EVENTS

A persistent AE is one that extends continuously, without resolution, between subject evaluation time points. Such events should only be recorded once on the SAE Report Form and/or the AE eCRF. If a persistent AE becomes more severe (changes from a Grade 1 or 2 AE to a Grade 3 or 4 AE) or lessens in severity (changes from a Grade 3 or 4 AE to a Grade 1 or 2 AE), it should be recorded on a separate SAE Report Form and/or AE eCRF.

A recurrent AE is one that occurs and resolves between subject evaluation time points, and subsequently recurs. All recurrent AEs should be recorded on an SAE Report Form and/or AE eCRF for each recurrence.

TGR-1202-201-CLL

10.8.2 ABNORMAL LABORATORY VALUES

Abnormal laboratory results should be noted in the eCRF as an adverse event if they are associated with an overdose, require or prolong inpatient hospitalization, or are otherwise considered clinically significant by the investigator. If an abnormal laboratory value or vital sign is associated with clinical signs and/or symptoms, the sign or symptom should be reported as an AE, and the associated laboratory value or vital sign should be considered additional information that must be collected in the relevant eCRF. If the laboratory abnormality is a sign of a disease or syndrome, only the diagnosis needs to be recorded on the SAE Report Form or AE eCRF.

